6.9.2. Interim Analyses

Given the relative small sample size, we will not perform interim analysis.

6.9.3. General statistics

All data will be managed by the LCC in conjunction with the Steering Committee. Data will be entered and reviewed on an ongoing basis. Key listings and tables will be defined by the Steering Committee. Tables, listings and raw data (as SAS transport files) will be made available to the members of the Steering Committee upon request.

The statistical analysis of the primary and all secondary efficacy endpoints will be performed in the modified Full Analysis Set (FAS), defined as all randomly assigned patients except those withdrawing informed consent for use of all trial data and in case many protocol violations are observed throughout the study, a Per Protocol Set (PPS) will be defined and all efficacy analyses will be repeated on the PPS.

All continuous data will be presented by treatment group using the number of non-missing observations, mean, standard deviation, median and (Q1,Q3). Categorical data will be presented by treatment group using the observed frequencies and percentages for each category.

The primary endpoint (% voxels with ADC < 0.650 mm²/s) will be analyzed by means of an analysis of variance (ANOVA) that includes randomized group and initial shockable rhythm as factors. The treatment effect will be estimated by the difference between treatment groups and presented along with its corresponding 95% confidence interval. Missing values for patients who die prior to the DW-MRI will be imputed on the basis of age, gender, presence of basic life support, presence of initial shockable rhythm, duration of advanced life support, neuron specific enolase, presence of a malign EEG pattern on day 1, final outcome at ICU discharge and allocated treatment arm.

Continuous and normally distributed secondary endpoints will be analyzed by means of an ANOVA including randomized treatment and initial shockable rhythm as factors in the model. Estimated treatment differences will be presented with their 95% confidence interval. Continuous secondary endpoints that show serious deviations from a normal distribution will be analyzed by means of a Van Elteren that includes the initial shockable rhythm as stratification factor. Binary secondary endpoints will be analyzed by means of a stratified Chi-squared test. Treatment differences will be expressed as risk ratios and presented along with their corresponding 95% confidence intervals.

Censored outcomes will be presented using Kaplan-Meier curves analyzed using a stratified long-rank test. The treatment effect will be expressed as a hazard ratio.

Prespecified subgroup analysis

Prespecified subgroup analysis will be performed for the primary endpoint according to age (> or <65 years), gender, time-to-ROSC (> or < 25 min), Initial rhythm (shockable or non-shockable), presence of bystander CPR (yes/no), presence of chronic hypertension (yes/no) and treatment center.

The interaction will be assessed using an analysis of variance.

The full statistical methods planned for this trial will be written as a separate document (Statistical Analysis Plan) prior to the completion of the study.

6.10. Changes in Conduct of the Study or Planned Analyses

Any change in the conduct of the study or planned analyses instituted after the start of the study will be documented. The date, time and reason for the change, the procedure used to decide on the change, the person or group responsible for the change and the nature and content of the data available when the change is made will be documented whether or not the change was documented as a formal protocol amendment.

7. MISCELLANEOUS

7.1. Case Report Forms

All case report forms will be electronic using Open Clinica, a web-based tool, provided by LCC. The site staff will enter and edit the data via a secure network, with secure access. An electronic audit trail will be maintained. The investigator will confirm the accuracy of the data by using an electronic signature. ZOL as a Study Center shall only provide coded or de-identified study data to the Sponsor.

7.2. Investigator Requirements

All investigators must be qualified by training and experience to undertake the proposed clinical trial, and assume responsibility for all aspects of the trial conducted at their investigative site.

Prior to study initiation, the investigator will complete and submit to LCC all documents required by ICH (E6) section 8.0. Additionally, each investigator must assure the following:

7.2.1. Study Staff Training

The study staff is qualified by training and experienced to assist with the proposed research. This training must be documented and maintained at the study site.

7.2.2. IEC Requirements

An IEC that complies with the requirements set forth in ICH (E6) section 3.0 will be responsible for the initial and continuing review and approval of the proposed clinical study.

7.2.3. IEC Reporting of Issues

Prompt reporting to the IEC all changes in research activity and all unanticipated problems involving risks to human subjects or others, and that he/she will not make any changes in the research until the IEC has approved the changes.

7.2.4. IEC Approvals

Reporting to IEC as required on the progress of the investigation and within three months after completion, termination or discontinuation of the study.

7.3. Recording of Adverse Events

Each patient/subject will be assessed for any new or continuing adverse events by the clinical investigator and the study coordinator during the intervention period. An adverse event is defined as any untoward medical occurrence in a patient/subject during the clinical trial. The event need not have a causal relationship with the treatment. This includes any events that are not seen at baseline or, if present at baseline, have worsened in severity. Any adverse event reported by the caregiver or noted by the investigator or study coordinator will be recorded on the Adverse Event pages on the case report form. The severity and drug relationship will be determined, and any management required will be recorded. The investigator will review the clinical laboratory test results in a timely fashion. Only those results qualifying as adverse events, as defined above, will be recorded on the Adverse Event section of the case report form. An effort will be made to determine the final outcome/resolution of adverse events that persist at the time of study completion.

7.3.1. Study treatment Relationship

The investigator is responsible for assessing the causal relationship between any events and the study treatment. Additionally, the investigator is responsible for providing appropriate treatment for the event and for adequately following the event until resolution. The clinical investigator should determine the relationship between the adverse event and the treatment using the following explanations:

Not Related

The event is clearly related to other factors such as the patient's/subject's clinical state, therapeutic interventions, or concomitant drugs administered to the patient/subject.

Unlikely

The event was most likely produced by other factors such as the patient's/subject's clinical state, therapeutic interventions or concomitant drugs administered to the patient/subject, and does not follow a known response pattern to the study treatment.

Possible

The event follows a reasonable temporal sequence from the time of drug administration and/or follows a known response pattern to the study treatment, but could have been produced by other factors such as the patient's/subject's clinical state, therapeutic interventions or concomitant drugs administered to the patient/subject.

Probable

The event follows a reasonable temporal sequence from the time of drug administration and follows a known response pattern to the study treatment and cannot be reasonably explained by other factors such as the patient's/subject's clinical state, therapeutic interventions or concomitant drugs administered to the patient/subject.

Definitely

The event follows a reasonable temporal sequence from the time of treatment administration and follows a known response pattern to the study treatment and cannot be reasonably explained by other factors such as the patient's/subject's clinical state, therapeutic interventions or concomitant drugs administered to the patient/subject and either occurs immediately following study drug administration, or improves on stopping the treatment.

Temporal sequence is defined as an association between the suspect treatment and the observed reaction or event in which the suspect treatment was started prior to the reaction or event as defined by history or blood level of drug.

Study drug(s) includes the drug(s) under evaluation, the reference drug(s), placebo, or any other drug(s) required by the protocol.

Severity of an adverse event will be defined from the qualitative assessment of the degree of intensity of the event as determined by the investigator or as reported to him/her by the patient/subject. The assessment of severity is made irrespective of treatment or seriousness of the event and should be evaluated according to the following scales:

1 = **Mild** - awareness of the symptom but easily tolerated

2 = **Moderate** - discomfort enough to interfere with normal activities

3 = **Severe** - Incapacitating with the inability to perform normal activities

7.3.2. Serious Adverse Events

A serious adverse event is defined as any event that at any dose: results in death, is life-threatening, results in persistent or significant disability / incapacity, requires or prolongs inpatient hospitalization, or is a congenital anomaly.

Important medical events that without medical or surgical intervention would also have resulted in one of the outcomes listed above are also considered a serious adverse event. Any serious adverse event must be reported on a Serious Adverse Event form to LCC within 24 hours of investigator becoming aware of the event by fax to:

Leuven Coordinating Centre

Fax to: [name]

The patient/subject must be monitored carefully until the condition disappears, reaches a clinically stable endpoint, and/or the etiology is identified. The initial telephone contact will be followed by detailed descriptions of the event and supported as needed with written copies of hospital case reports, autopsy reports, and other appropriate documents.

Follow-up information (including information requested by the Sponsor) should be reported within 24-hours. All serious, related and unexpected adverse events will be sent from LCC to the principal investigator (blind maintained), who will forward these reports to their IEC. All serious adverse events will also be

distributed to the Data Safety and Monitoring Board and other investigative sites. Serious adverse events will be recorded during the period of study drug administration.

7.3.3. Unexpected Adverse Events

An unexpected adverse event is any event that is not identified in nature, severity or frequency in the current study protocol.

7.4. Records Retention

In compliance with GCPs and ICH Guidelines, copies of all records (e.g., informed consent documents, laboratory data slips, source documents, IND safety reports, test article dispensing records, etc.) which support case report forms of this study, must be retained in the files of the responsible investigator for a minimum of two years following notification by LCC that all investigations at all sites are completed, terminated, or discontinued. If the investigator retires, relocates, or for other reasons withdraws from the responsibility of keeping the study records, custody must be transferred to a person who will accept the responsibility. LCC must be notified in writing of the name and address of the new custodian.

7.5. Monitoring

The study will be periodically monitored by a CRA. It is the responsibility of the principal investigator to provide all study records, including case report forms, source documentation, etc., to the monitor at their visit.

7.6. Amendments to the Protocol

Neither the investigator nor the Steering Committee will amend or modify the protocol without written notification of the other. All amendments must be approved by the Steering Committee prior to implementation. All amendments must be submitted to the IEC as required. The IEC must approve major amendments prior to implementation at the study site.

7.7. Termination of Trial

It is agreed that, for reasonable cause, either the investigator or the Steering Committee may terminate this study, provided written notice is submitted at a reasonable time in advance of intended termination.

7.8. Insurance

In accordance with the LEH Sponsor shall assume, even without fault, the responsibility of any damages incurred by a study Subject and linked directly or indirectly to the participation to the study, and shall provide compensation therefore through its insurance.

7.9. Intellectual Property

Unless arranged for otherwise in the IWT grant agreement, Study Centers expressly agree that each Study Center shall remain the owner of its source data and results it generates pursuant to the study. In the event of joint results the Study Centers shall have joint property thereof

## 1 Purpose

This document provides a detailed description of the statistical analyses prescribed in the final protocol (version 4, dated 20Jan2017), that will be performed for the evaluation of the primary safety, secondary efficacy, clinical and safety endpoints of the NEUROPROTECT study.

## 2 Study Objectives and Endpoints

### 2.1 Study Objective

The **primary objective** of the trial is to assess acute whether or not a new goal-directed hemodynamic optimization strategy can reduce cerebral ischaemia in post-cardiac arrest (CA) patients as quantified by diffusion weighted MRI (DW-MRI) to be performed at day 4-5 with quantification of the percentage of ischaemic voxels with an apparent diffusion coefficient (ADC) below 0.650 mm^2/s.

### 2.2 Study Endpoints

#### 2.2.1 Primary Target Variable

% of ischaemic voxels with an ADC<0.650 mm^2/s on 4-5 day DW-MRI.

#### 2.2.2 Secondary Efficacy Variables

% of patients with CPC 3-5 at discharge from ICU.

% of patients with CPC 3-5 at 180 days post-CA

SF-36 questionnaire at 180 days post-CA: total score and subscales

Neurocognitive testing at discharge from the hospital: total percentile scores of the Wechsler Memory Scale

Biomarkers – neuron-specific enolase on days 1 to 5.

Activities Daily Life (ADL) score at discharge from the hospital

6-minute walking distance (6MWD) [m] at discharge from the hospital

Renal function: creatinine [mg/dL] and urinary output [mL/24h] at days 1 to 5.

Length of ICU stay

Duration of mechanical ventilation

Placement of tracheostomy

#### 2.2.3 Safety Variables

% of patients with life threatening arrhythmias during intervention period

- % of patients with new onset atrial fibrillation during intervention period
- % of patients with pulmonary congestion requiring diurectics during intervention period

### 3 Study Methods

#### 3.1 Overall Study Design and Plan

This was a prospective, multicentre, interventional, controlled, randomized, open-label investigator-driven study.

Patients were recruited at 2 tertiary care hospitals in Belgium (UZ Leuven and ZOL-Genk) and were randomized in a 1:1 ratio to either goal-directed hemodynamic optimization or standard care. In patients randomized to receive the intervention, the target mixed venous oxygen saturation (SVO2) was between 65-75% and the target mean arterial pressure (MAP) was between 85- 100mmHg. Fluid administration and hemodynamic support was adjusted according to a flow chart in case SVO2 or MAP were below or above the suggested targets on an hourly basis. The intervention lasted up to 36 hours after admission to ICU.

Once admitted to ICU, the patients were assessed hourly up to 36 hours after admission and daily up to 5 days after admission. Further assessments were done at discharge from ICU, discharge from the hospital and at 180 days after the initial cardiac arrest.

#### 3.2 Selection of Study Population

All patients presenting or referred to the investigational site after being successfully resuscitated from out-of-hospital cardiac arrest were screened for enrollment. All enrolled patients were expected to meet all inclusion and exclusion criteria.

#### 3.3 Method of Treatment Assignment and Randomisation

Randomization was performed by site and was stratified according to the presence of shockable rhythm.

Randomization was available daily for 24 hours via a centralized telephone Interactive Voice Response System (IVRS) at the LCC.

#### 3.4 Blinding of Study Treatment

Health care professionals caring for the patients were aware of the intervention assignment. However, physicians performing neurological prognostication, radiologists interpreting MRIs, study personnel assessing final outcome and the study

statistician were kept unaware of the randomized group up to the moment of the unblinding of the study after database lock.

## 4 Sequence of Planned Analyses

### 4.1 Interim Analyses

No interim analysis was planned.

A Data Monitoring Committee reviewed the data on a regular basis. The primary responsibility of the DSMB was to review the progress and conduct of the trial in order to maintain scientific rigor and to ensure the well being of patients participating in the trial.

### 4.2 Final Analysis and Reporting

Upon final database lock, statistical analyses of the data will be performed according to the methods described in this document.

Any deviations will be documented.

The analysis populations were finalised at a Blinded Review Meeting on 5Mar2018 that was held by the Steering Committee upon inclusion of all patients into the study. The decisions made at this meeting were documented in the Analysis Sets document.

## 5 Sample Size Determination

Based on the results of a pilot study at Stanford University in which the standard deviation of the percentage  $ADC < 0.650 \text{ mm}^2/\text{s}$  in comparable post-CA patients was 8.9%, it was estimated that 56 patients would be necessary in each study group to show a 40% reduction in the extent of cerebral ischemia with a power of 80% at a two-sided alpha level of 0.05.

## 6 Analysis Populations

### 6.1 Safety Set (SS)

The safety analysis set will include all patients who have received at least one dose of study medication.

The safety set will be used for the analysis of all safety data. Summaries will be done by actual rather than randomised treatment.

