6.3. Selection of Study Population

All patients presenting or referred to the investigational site after being successfully resuscitated from out of hospital CA will be screened for enrolment. All patients will be expected to meet all inclusion and exclusion criteria before entering the study. Minor deviations to these criteria may be allowed with prior approval of the principle investigator of the study site.

6.3.1. *Inclusion Criteria*

The patient must meet the following criteria:

1. Out-of-hospital CA of presumed cardiac cause irrespective of the presenting rhythm
2. Unconsciousness (Glasgow coma scale < 8) at hospital admission
3. Age \geq 18 years
4. Sustained return of spontaneous circulation (ROSC) (=when chest compressions have not been required for 20 consecutive minutes)

6.3.2. *Exclusion Criteria*

Exclusion Criteria:

1. Suspected or confirmed intracranial bleeding or stroke
2. Known limitations in therapy or Do Not Resuscitate-order
3. Known disease compromising 180 day survival
4. Known pre-CA cerebral performance category 3-4
5. Previous stroke (TIA can be included)
6. MRI incompatible cardiac or neurosurgical device
7. Systolic blood pressure < 90 mmHg on norepinephrine > 1 mcg/kg/min).
8. Open chest
9. ECMO (extracorporeal membrane oxygenation)
10. Pregnancy

6.3.3. *Withdrawal of Patients from Therapy or crossover*

In the intervention (“Neuroprotect post-CA”) group, a reduction in vasopressor doses to maintain a MAP of 65mmHg is recommended if any of the pre-specified serious adverse events that were potentially related to an increased rate of vasopressor infusion occurs. These events include: major ventricular arrhythmia requiring life support, electrical or pharmacological cardioversion, poorly tolerated supraventricular arrhythmia and peripheral limb ischemia.

Treatment may also be discontinued if the legal representative withdraws their consent.

All patients who are withdrawn from study treatment will have safety assessments completed during the entire course of the study.

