6.8. Efficacy and Safety Variables

6.8.1. Duration of Participation

It is expected that patients will participate in this study for 180 days, including 36 hours of treatment with study drug, cardiac MRI at day 4-5 and clinical follow-up until 180 days after CA.

Adverse events will be recorded during the period of study drug administration.

Visit schedule overview:

- At ICU discharge:
 - Cerebral performance category score
 - Length of ICU stay
 - Length of mechanical ventilation
 - Tracheostomy (yes/no)

- At hospital discharge
 - Cognitive testing
 - ADL
 - 6 MWD
 - Cerebral performance category score
- At 180 days post-CA
 - Cerebral performance category score
 - SF36

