## 11.6 Safety Outcomes

The number (%) of patients with safety outcomes (i.e. incidence of life-threatening arrhythmias, limb ischaemia, new onset atrial fibrillation, pulmonary congestion requiring diuretics) will be presented by actual group for the SS.

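### Do the undefined terms for the Safety Set and the actual treatment group, and the missing window for limb ischaemia, make the safety table unreliable?

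*SAP*

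**What the plan says.** SAP 6.1 sets the entry rule, "The safety analysis set will include all patients who have received at least one dose of study medication", and the grouping rule, "Summaries will be done by actual rather than randomised treatment". SAP 11.6 repeats the grouping: the number and percentage of patients with life-threatening arrhythmias and with "limb ischaemia, new onset atrial fibrillation, pulmonary congestion requiring diuretics) will be presented by actual group for the SS". That makes four outcomes. SAP 2.2.3 lists only three, each tied to the intervention period; the first is the percentage "of patients with life threatening arrhythmias during intervention period". Limb ischaemia is not among them.

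Protocol 6.3.3, whose heading covers both withdrawal and crossover, says that in the intervention group "a reduction in vasopressor doses to maintain a MAP of 65mmHg is recommended if any of the pre-specified serious adverse events" thought related to more vasopressor infusion occurs. The listed events include major ventricular arrhythmia and peripheral limb ischaemia. The same section adds: "All patients who are withdrawn from study treatment will have safety assessments completed during the entire course of the study".

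On exposure and recording, Protocol 6.8.1 states: "It is expected that patients will participate in this study for 180 days, including 36 hours of treatment with study drug". It continues: "Adverse events will be recorded during the period of study drug administration".

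**The concern.** The Safety Set wording suits a drug trial. Here patients are randomised to strategies, and haemodynamic support in the control arm is left to the treating physician around a MAP of 65 mmHg. No particular first dose marks entry. An intervention patient with both MAP and mixed venous saturation in range also gets no drug step from the flow chart. Read narrowly, the entry rule could drop patients from either arm.

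The grouping rule looks more serious. Only the intervention arm has a rule that moves a patient to the control arm's MAP value, and events of the kind in the safety table trigger it. If actual treatment meant the target in force after the reduction, the event itself would send the patient to the control column. The error would run one way and hide harms that the Protocol itself links to vasopressor dose.

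Last, limb ischaemia has no window of its own in the SAP. The Protocol's sentence on withdrawn patients could suggest follow-up to 180 days for some patients and 36 hours for the rest.

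**Working it through.** There is no stated figure in the plan to reproduce, so the check is mainly a reading of the passages together.

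**1. Who enters the Safety Set.** Protocol 7.3.1 explains study drug broadly, so that any drug the Protocol requires counts. Protocol 6.8.1 speaks of 36 hours of study drug for patients in general, not for one arm. Protocol 6.5.3 gives all patients basic glucose and crystalloid infusions, and sedation where it is tolerated. On that meaning essentially all of the planned 2 × 56 = 112 patients enter, by the same route in both arms. The narrow reading (vasopressor or inotrope only) goes against 7.3.1.

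**2. What actual group can mean.** The reduction to MAP 65 mmHg appears in Protocol 6.3.3 and again in 6.5.1, and both places introduce it as a rule for the intervention group. It concerns vasopressor dose. Nothing in either place ends the saturation target or the pulmonary artery catheter monitoring, so the patient is not thereby on standard care. The triggering event also comes before the reduction: even counting by the target in force at the time of the event leaves it with the intervention. Protocol 7.3.1 likewise looks to the treatment started before the event. Moving the event to control requires backdating a later target.

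**3. What the strained reading would do.** The documents give no event rates, so these counts are assumptions, with 56 per arm from SAP 5. If *a* intervention and *b* control patients have the event and *k* intervention event patients are relabelled, the risk difference is (a − k)/(56 − k) − (b + k)/(56 + k).

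- 11 v 6, k = 0: 11/56 − 6/56 = +8.9 points.
- 11 v 6, k = 1: 10/55 − 7/57 = +5.9 points, a change of −3.0.
- 12 v 6, k = 6: 6/50 = 12.0% against 12/62 = 19.4%, a reversal from 21.4% against 10.7%.

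Grouping by strategy started means k = 0 and no change. SAP 11.6 plans only counts and percentages, with no test.

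**4. The window for limb ischaemia.**

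| Place | Covers | Period |
|---|---|---|
| SAP 2.2.3 | three outcomes | intervention period |
| SAP 11.6 | four outcomes | none restated for any of them |
| Protocol 6.6.3 | all four, hourly, all patients | treatment period (heading of 6.6) |
| SAP 3.1 | hourly assessment | up to 36 hours after ICU admission |
| Protocol 6.8.1, 7.3 and 7.3.2 | adverse and serious adverse events | intervention or study drug period |
| Protocol 6.8.1, visit schedule | ICU discharge, hospital discharge, day 180 | no limb ischaemia or adverse event item |

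The nominal contrast is 180 × 24 = 4,320 hours against 36, a factor of 120, but no scheduled collection of limb ischaemia stands behind the longer figure. The data for all four outcomes come from the same hourly form over the same 36 hours in both arms.

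**The case for a change.** The best case for a change is that the terms really are undefined, the ambiguity is tied to the outcome and affects one arm only, and a few words would close it. The word crossover in the heading of Protocol 6.3.3 gives the unfavourable reading some footing. An event that occurs after a reduction is also less clear-cut than the one that triggered it. The generic passage in Protocol 7.3.1 mentions placebo, which this trial does not have, so it was not written with this design in mind. SAP 4.2 says that the analysis populations were settled at the blinded review on 5 March 2018, yet the SAP reports decisions from it only for the Full Analysis Set and the Per Protocol Set.

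The textual points stand. They do not show that the plan, followed as written, gives a wrong table. SAP 11.6 counts patients, so each patient belongs to one group, and that is naturally the strategy begun; this covers later events as well. A single word in a heading does not outweigh two passages that keep the rule inside the intervention arm. The group and set definitions may also be in the Analysis Sets document, which is not available here.

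One tension in the Protocol is genuine. The sentence in 6.3.3 on withdrawn patients does not sit easily with the recording period in 6.8.1, 7.3 and 7.3.2, and it is not said whether a target reduction counts as withdrawal. Those passages should be reconciled for the record, but the table in SAP 11.6 does not depend on it.

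**Conclusion.** No change to the plan follows. The wording is borrowed from drug trials, and limb ischaemia was left off the list in SAP 2.2.3. Both are gaps that an analyst with the Protocol at hand fills in one sensible way: all patients in whom a strategy was started, grouped by that strategy, with all four outcomes over the intervention period. Under that reading no event changes group, the Safety Set is essentially complete, and the window is the same in both arms.

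This rests on three assumptions: study drug carries its broad Protocol meaning, the hourly form is the source for limb ischaemia, and the Analysis Sets document does not adopt a different grouping. The shifts of about 3 points per relabelled patient rest on invented counts and on a reading that the Protocol does not support, so they do not measure a flaw in the plan. Writing the definitions out would be tidy but would not alter the table.
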